2.1 Primary estimands

An estimand is a precise description of the treatment effect reflecting the clinical question posed by the trial objective. It summarizes at a population-level, what the outcomes would be in the same patients under each of the treatment conditions being compared. Attributes of an estimand include the population, variable (or endpoint) and treatment of interest. It also specifies how intercurrent events are addressed and provides a population-level summary for the variable. The structured framework of estimand detailed in ICH E9 (R1) was newly adopted by the Regulatory Members of the ICH Assembly under Step 4 in Nov-2019.

The clinical question of interest is: What is the difference between IV cipargamin and IV artesunate in early reduction of asexual parasite load in participants with severe *P. falciparum* malaria who are treated with at least one dose of IV treatment?

The justification for targeting this treatment effect is that severe *P. falciparum* malaria is caused by asexual parasite burden, leading to sequestration and microvascular obstruction. Rapid reduction of *P. falciparum* asexual parasites by 12 hours should prevent participants from further deterioration, and so allow eventual recovery from the disease.

The primary estimand is described by the following attributes:

1. Population: Participants with severe *P. falciparum* malaria and who have been treated with at least one dose of IV study medication (either cipargamin or artesunate). Further details about the population are provided in [Section 5](#).
2. Variable: A binary outcome indicating $\geq 90\%$ reduction in *P. falciparum* parasite at 12 hours (H12) after first IV dose as compared to baseline.
3. Treatment of interest: IV cipargamin vs IV artesunate. Further details about cipargamin and artesunate are provided in [Section 6](#).
4. Intercurrent events: (1) taking IV rescue antimalarial medication prior to H12 parasite assessment, or (2) mortality prior to H12 parasite assessment. Details on how to handle the intercurrent event are provided in [Section 12.4.3](#).
5. Summary measure: Difference in proportion of participants with $\geq 90\%$ reduction in baseline parasite count between IV cipargamin dose regimen and IV artesunate will be

evaluated within each cohort separately except Cohort 1, which will be combined with Cohort 2.

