2.2 Secondary estimands

The secondary clinical question of interest is: What is the difference between IV cipargamin and IV artesunate in clinical success at 48 hours without the need of IV rescue antimalarial medication?

[figure not shown]
The justification for the secondary estimand is that it will reflect the clinical outcome including recovery from the most severe symptoms of the disease with IV treatment before earliest possible administration of oral antimalarial medication at 48 hours. This objective is being evaluated for possible use in Phase III study. Further details can be found in [Section 12](#).

The secondary estimand is described by the following attributes:

1. Population: participants with severe *P. falciparum* malaria and treated with at least one dose of IV study medication. Further details about the population are provided in [Section 5](#).
2. Variable: A binary outcome indicating clinical success- participant is alive and has absence of asexual parasites and no critical signs of severe malaria (See [Section 8.3.1.2](#) for further details) at 48 hours.
3. Treatment of interest: IV cipargamin vs IV artesunate. Further details about cipargamin and artesunate are provided in [Section 6](#).
4. Intercurrent event: receive IV rescue antimalarial medication before assessing the clinical success prior to H48.
5. Summary measure: Proportion of participants with clinical success with 90% CI within a treatment group as well as the difference between the cipargamin and artesunate treatment group.

3 Study design

Figure 3-1 Study design

Notes:

KAE609 (Cipargamin)

Moderately severe malaria – Prostration and/or repeated vomiting (Barnes et al 2004)

Study to progress from Cohort 1 to Cohort 2 without interruption if none of the KAE609 arms in Cohort 1 meets the stopping criteria.

*Results from Cohort 1 and Cohort 2 will be analyzed to determine the safe and efficacious exposure range and the corresponding doses (KAE dose regimen 3) for participants in Cohorts 3 to 5.

Doses for Cohort 4 will be confirmed after PK analysis from upto 6 KAE609 participants from Cohort 3 and for Cohort 5, it would be post completion of Cohort 4 .

** Cohort 5 recruitment is dependent on availability of adequate toxicology package to dose down to ≥ 6 m

KAE609 doses across the study will be adaptive depending on the safe and efficacious exposure range identified before the study (for Cohorts 1-2) and after interim assessment of Cohort 1 & 2 (for Cohorts 3-5)

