5.1 Inclusion criteria

Participants eligible for inclusion in this study must meet **all** of the following criteria:

1. Cohort 1: Participants aged ≥ 12 years with moderately severe malaria as defined in [Barnes et al \(2004\)](#) (prostration and/or repeated vomiting) without presence of other signs of severe malaria ([Section 16.4](#)) and with high *P. falciparum* parasitemia (60,000-250,000 parasites per μ l).

Subsequent Cohorts 2 to 5: Participants diagnosed with severe malaria as defined in [Section 16.4](#) (modified version of severe malaria criteria in [WHO 2014](#)) and *P. falciparum* parasite count of ≥ 5000 per μ l

Cohort 2: Participants aged ≥ 12 years

Cohort 3: Participants aged 6 - <12 years

Cohort 4: Participants aged 2 - < 6 years

Cohort 5: Participants aged ≥ 6 months - <2 years

2. Written informed consent form must be obtained prior to any study related procedure. If the participant is unable to read and write or otherwise incapable of signing an informed consent, then a witnessed consent according to local ethical standards is permitted (formally documented and witnessed, ideally via an independent trusted witness). Participants aged < 18 years, who are capable of providing assent, must provide assent with parental/legal guardian consent or as per local ethical guidelines. The participant or parent/legal guardian (in case of pediatric participants) is able to understand and comply with protocol requirements, instructions and protocol-stated restrictions for their child and is likely to complete the study as planned.

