12.1 Analysis sets

The analysis includes the following data sets:

- Randomized set: all participants who are randomized.
- Full analysis set (FAS): the FAS will be comprised of all participants from Randomized set that have baseline *P. falciparum* count > 0 and take at least one dose of IV study treatment during the treatment period. Following the intent-to-treat principle, participants will be analyzed according to the treatment group assigned at randomization.
- Per-protocol set (PPS): Participants in the FAS who satisfy the inclusion criterion for severe malaria and do not have protocol deviations that impact on efficacy.
- Safety set (SS): All participants who take at least one dose of study drug during the treatment period. Participants will be analyzed according to treatment received.
- PK analysis set: All participants who have at least one valid (i.e. not flagged for exclusion) PK concentration measurement, receive at least one dose of study drug, and do not have any protocol deviations that impact on PK data.

Full details will be described in the statistical analysis plan (SAP). Important protocol deviations for exclusion from PPS or PK analysis set will be identified by the clinical team before Cohort 1 and 2 database lock and the final database lock.

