12.4.2 Statistical model, hypothesis, and method of analysis

The statistical null hypothesis is that the difference in proportion of participants with $\geq 90\%$ reduction at 12 hours between a cipargamin dose regimen and artesunate is ≤ -0.1 with the alternative hypothesis that the difference is > -0.1 .

The statistical hypothesis will be tested at the 2-sided 10% significance level without multiplicity adjustment for multiple comparison due to multiple cipargamin dose regimen. Two-sided 90% confidence intervals (CI) for the difference between each cipargamin dose regimen vs artesunate will be provided using the Wilson uncorrected method based on FAS; a cipargamin dose regimen is said to be non-inferior to artesunate if the lower limit of CI is > -0.1 .

The hypothesis will be tested for each Cohort separately except Cohort 1, which will be combined with Cohort 2.

Data from participants in Cohorts 1 and 2 will be pooled together to allow evaluation of non-inferiority to artesunate since both cohorts include participants aged ≥ 12 years although participants in Cohort 1 are milder in clinical condition compared to participants in Cohort 2. The underlying assumptions are (1) the participants for each treatment group follow a binomial distribution separately in each Cohort separately except Cohort 1, which will be combined with Cohort 2 (2) participants for each treatment group, follow the same binomial distribution in Cohorts 1 and 2.

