- For **height in cm** and **SCr in mg/dL**: $\text{eGFR (ml/min/1.73 m}^2\text{)} = 0.413 \times (\text{height/SCr})$
- For **height in cm** and **SCr in $\mu\text{mol/L}$** : $\text{eGFR (ml/min/1.73 m}^2\text{)} = 36.5 \times (\text{height/SCr})$

Normal renal GFR values, as measured by inulin clearance ([Schwartz and Furth 2007](#)), are provided in [Table 16-4](#) below:

Table 16-4 **Normal GFR in children and young adults, as assessed by inulin clearance (adapted for pediatric participants included in this study)**

Age	Mean GFR \pm SD (ml/min per 1.73 m ²)
Term babies	
4-6 months	87.4 \pm 22.3
7-12 months	96.2 \pm 12.2
1-2 years	105.2 \pm 17.3
Children	
3-4 years	111.2 \pm 18.5
5-6 years	114.1 \pm 18.6
7-8 years	111.3 \pm 18.3
9-10 years	110.0 \pm 21.6
11-12 years	116.4 \pm 18.9
13-15 years	117.2 \pm 16.1
2.7-11.6 years	127.1 \pm 13.5
9-12 years	116.6 \pm 18.1
Young adults	
16.2-34 years	112 \pm 13

16.3

CCI

Table 16-5

CCI

CCI

16.4 Appendix 4: Modified version of WHO classification of signs of severe *P. falciparum* malaria

Severe malaria is defined as occurrence of one or more of the following observations, in the absence of an identified alternative cause, and in the presence of *P. falciparum* asexual parasitemia (WHO 2014)

Table 16-6 Definition of severe malaria

Signs	Definition
Impaired consciousness	A Glasgow Coma Score < 11 in adults or a Blantyre coma score < 3 in children
Prostration	Generalized weakness so that the person is unable to sit, stand or walk without assistance
Multiple convulsions	More than two episodes within 24 hours
Acidosis*	venous plasma lactate ≥ 4 mmol. Severe acidosis manifests clinically as respiratory distress – rapid, deep and laboured breathing
Hypoglycaemia	Blood or plasma glucose < 2.2 mmol (< 40 mg/dL)
Severe malarial anaemia	A haemoglobin concentration < 5 g/dl or a haematocrit of < 15% in children < 12 years of age (< 7 g/dl or < 20%, respectively, in adults) together with a parasite count > 10,000/ μ l
Renal impairment (acute kidney injury)**	Plasma or serum creatinine > 265 μ mol/L (3 mg/dL) or ≥ 3 x ULN or blood urea > 20 mmol/L
Jaundice	Plasma or serum bilirubin > 50 μ mol/L (3 mg/dL) with a parasite count > 100,000/ μ l
Pulmonary edema	Radiologically confirmed, or oxygen saturation < 92% on room air with a respiratory rate > 30/min, often with chest indrawing and crepitations on auscultation

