2.5 Analysis of the primary objective

2.5.1 Primary Estimand

An estimand is a precise description of the treatment effect reflecting the clinical question posed by the trial objective. It summarizes at a population-level, what the outcomes would be in the same patients under each of the treatment conditions being compared. Attributes of an estimand include the population, variable (or endpoint) and treatment of interest. It also specifies how intercurrent events are addressed and provides a population-level summary for the variable. The structured framework of estimand detailed in ICH E9 (R1) was newly adopted by the Regulatory Members of the ICH Assembly under Step 4 in Nov-2019.

The clinical question of interest is: What is the difference between IV cipargamin and IV artesunate in early reduction of asexual parasite load in patients with severe *P. falciparum* malaria who are treated with at least one dose of IV treatment?

The justification for targeting this treatment effect is that severe *P. falciparum* malaria is caused by asexual parasite burden, leading to sequestration and microvascular obstruction. Rapid reduction of *P. falciparum* asexual parasites by 12 hours should prevent patients from further deterioration, and so allow eventual recovery from the disease.

The primary estimand is described by the following attributes:

1. Population: Patients with severe *P. falciparum* malaria and who have been treated with at least one dose of IV study medication (either cipargamin or artesunate). Further details about the population are provided in Section 5 in the protocol.
2. Variable: A binary outcome indicating $\geq 90\%$ reduction in *P. falciparum* parasite at 12 hours (H12) after first IV dose as compared to baseline. A patient is considered as achieving primary endpoint if *P. falciparum* asexual parasite reading at 12 hours is either absent or with a positive value that is $\leq 10\%$ of the baseline value.
3. Treatment of interest: IV cipargamin vs IV artesunate. Further details about cipargamin and artesunate are provided in Section 6 in the protocol .
4. Intercurrent events: (1) taking IV rescue antimalarial medication prior to H12 parasite assessment, or (2) mortality prior to H12 parasite assessment. Details on how to handle the intercurrent event are provided in [Section 2.5.3](#).

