5.9 Rule of exclusion criteria of analysis sets

Table 5-15 Protocol deviations and non-PD criteria leading to exclusion from analysis sets

Analysis Set	PD (Description and ID) that causes Patients to be excluded	Non-PD criteria that cause Patients to be excluded
Randomized	
 Informed Consent for study participation or parental consent not obtained and patient entered trial (INCL02) 	
 Not randomized
FAS	NA	
 Not in Randomized set Misrandomized if identified from IRT Baseline parasitaemia count is 0 or missing using local lab (central lab in case local lab is not available) No study drug taken
PPS	
 Not severe malaria for Cohort 2-5 (INCL01b) and not moderately severe malaria for Cohort 1 (INCL01a_1) Concomitant antimalarial medications (COMD01) if received before assessing the primary endpoint at 12 hours Unacceptable prior antimalarial drugs within 12 hours of screening (EXCL01.02) 	
 Not in FAS; Baseline Parasite species is other than Plasmodium falciparum OR mixed infection using local lab (central lab in case local lab is not available) Baseline Plasmodium falciparum parasite count <60000/uL or >250000/uL for cohorts 1-2 or <5000/ uL for cohorts 3-5 at using local lab (central lab in case local lab is not available)
SAF	NA	
 Not in Randomized set; No study drug taken
PK	
 Patients who received concomitant prohibited medication which may have an impact on PK exposure (COMD04) 	
 Not in SAF No evaluable pharmacokinetic parameter data Did not take at least on dose of IV study drug

6 Reference

Anne Lott & Jerome P. Reiter (2018): Wilson Confidence Intervals for Binomial Proportions With Multiple Imputation for Missing Data, *The American Statistician*, <https://doi.org/10.1080/00031305.2018.1473796>

Artesunate Package Insert. Ipca Laboratories Limited; Sep-2019.

Brand, J. P. L. (1999). Development, Implementation, and Evaluation of Multiple Imputation Strategies for the Statistical Analysis of Incomplete Data Sets. Ph.D. thesis, Erasmus University.

Brookmeyer, R. and Crowley, J. (1982) A confidence interval for the median survival time. *Biometrics*, 38, 29-41. <https://doi.org/10.2307/2530286>

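### Both estimands name severe malaria, but the analysed population includes vomiting-only Cohort 1 patients who are not severe by the trial's definition, and the protocol and SAP disagree on whether the per-protocol set keeps them

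*Protocol*

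**What the plan says.** **Estimands.** The primary population in Protocol 2.1 is "Participants with severe *P. falciparum* malaria and who have been treated with at least one dose of IV study medication", and SAP 2.5.1 repeats it. The key secondary population in Protocol 2.2 is "participants with severe *P. falciparum* malaria and treated with at least one dose of IV study medication", and SAP 2.6.1 repeats that. The objectives in Protocol section 2 are wider and cover moderately severe as well as severe malaria.

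**Who is enrolled.** Cohort 1 takes patients aged 12 and over with moderately severe malaria ("prostration and/or repeated vomiting) without presence of other signs of severe malaria") and 60,000 to 250,000 parasites per µl (Protocol 5.1). Table 16-6 in Protocol 16.4 opens with "Severe malaria is defined as occurrence of one or more of the following observations". It lists prostration but not vomiting. Protocol 5.2 excludes from Cohorts 2 to 5 anyone whose only qualifying feature is repeated vomiting.

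**Who is analysed.** The FAS requires a baseline count above zero and one IV dose (Protocol 12.1, SAP 2.2). Cohort 1 is pooled with Cohort 2 for the non-inferiority test, "although participants in Cohort 1 are milder in clinical condition compared to participants in Cohort 2" (Protocol 12.4.2).

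**Per-protocol set.** Protocol 12.1 defines it as "Participants in the FAS who satisfy the inclusion criterion for severe malaria and do not have protocol deviations that impact on efficacy". SAP 2.2 drops the severity clause and points to Table 5-15, where the disease-related exclusion is "Not severe malaria for Cohort 2-5 (INCL01b) and not moderately severe malaria for Cohort 1 (INCL01a_1". SAP section 4, on changes to protocol-specified analyses, reads None.

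**The concern.** The estimand population should describe the patients whose data enter the estimate. Here the stated population is narrower than the analysed one, and the objectives in the same protocol already use the wider wording. A reader of the age 12 and over result would take it as a result in severe malaria, although some contributing patients may not have had it by the trial's own table.

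The per-protocol conflict is separate. The PPS repeats the primary, sensitivity and supplementary analyses (Protocol 12.4.7, SAP 2.5.7) and the clinical-success analysis (SAP 2.6.6). If the protocol wording is applied as written, its membership differs from what the SAP would program, with no declared change to explain the difference. Timing makes this more than tidying. SAP 1.1 shows that Cohorts 1 and 2 were complete when it was written, and Protocol 6.4 unblinds the trial team to them after the interim lock. Two available rules for data that may already be known are hard to defend unless the choice is dated and both results are shown.

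**Working it through.** **1. The plan's own sizes.** Protocol 12.8.2 gives 6 + 14 + 38 + 38 + 20 = 116 randomised per arm, for 107 evaluable. Exact enumeration of the 90% Wilson-uncorrected interval at a true proportion of 0.75 in both arms gives a probability of a half-width of at most 0.1 of 0.790 at n = 106 and 0.838 at n = 107. So 107 reproduces, and 107/0.92 = 116.3. The primary figure of 13 per group cannot be checked independently because the cipargamin rate is redacted. A back-solved 85% against 45% returns 13, but 85% is not a document value.

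**2. Which Cohort 1 patients are affected.**

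| Cohort 1 patient | Severe by Table 16-6? | FAS | SAP PPS (severity rule) | Protocol PPS, read literally |
|---|---|---|---|---|
| Prostrated | Yes | In | In | In, or out if only the Cohort 2-5 limb of criterion 1 counts |
| Repeated vomiting only | No | In | In | Out |

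Only a loose reading of Protocol 12.1, in which each patient need only meet the disease criterion of his or her own cohort, agrees with the SAP.

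**3. Size.** All of Cohort 1 is 6/20 = 30% of each arm in pooled Cohorts 1 and 2, and 6/116 = 5.2% of each arm in pooled clinical success. These are ceilings, because the documents do not give the vomiting-only share. From the severity rule alone, the SAP PPS for the pooled comparison has 20 per arm and the protocol PPS 14 to 20: a difference of 0 to 6 per arm, or 0 to 18 over three arms. At the extreme the interval widens by a factor of about sqrt(20/14) = 1.195.

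**4. Does pooling help or hurt the non-inferiority claim?** Assume artesunate at 45% in Cohort 2 (SAP 3.1), cipargamin 20 points lower at 25%, no difference in Cohort 1, and a Cohort 1 response between 45% and 100% in both arms. The pooled true difference is 0.7 × (−20) + 0.3 × 0 = −14 points. Exact enumeration with the planned interval and the −0.1 margin gives these chances of declaring non-inferiority:

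- Cohort 2 alone, n = 14: 1.7%
- Pooled, n = 20: 0.8% to 3.2% over that range, and 1.2% when Cohort 1 response is 90%

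With a benefit instead (85% against 45% in Cohort 2, the 85% being assumed) and still no difference in Cohort 1, the chance is 0.91 for Cohort 2 alone and 0.82 to 0.92 pooled. The effect can go either way and is mostly a loss for cipargamin in the second case.

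**5. Would dropping Cohort 1 be a better repair?** For pooled clinical success it would leave 110 × 0.92 = 101 evaluable per arm, and the precision probability would fall from 0.838 to 0.545. Correcting the population wording avoids that loss.

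**6. A neighbouring rule.** The same PPS row of Table 5-15 applies the 60,000 to 250,000/µl window to Cohorts 1 and 2 together, although Cohort 2 eligibility is 5,000/µl or more (Protocol 5.1). As written, the SAP PPS keeps non-severe Cohort 1 patients and removes eligible severe Cohort 2 patients outside the window.

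**The case against.** The pooling is open. Protocol 12.4.2 gives its reason, admits the difference in severity and states the common-binomial assumption. Protocol 12.4.5 tests that assumption with separate intervals for Cohorts 1 and 2, and SAP 2.5.7 repeats those on the PPS. Both estimands refer to Protocol section 5 for population details, and that section includes Cohort 1. On the PPS, Protocol 12.1 leaves full details to the SAP, inclusion criterion 1 is a single item covering all cohorts, and the SAP applies it cohort by cohort without ambiguity. The PPS is only supportive in a Phase II dose-finding trial.

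Most of this stands, and it limits the point. The intention to include Cohort 1 is clear, the SAP rule is the natural one to keep, and a Cohort 2-only estimate exists for both analysis sets. It does not make the estimand wording correct, because a pointer to section 5 does not turn vomiting-only patients into severe cases under Table 16-6. Nor does deferring details to the SAP account for a severity clause that disappears while the SAP declares no change.

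**Conclusion.** The point holds as a mismatch of definitions. The estimand population is narrower than the analysed one, and the protocol's PPS rule, read literally, conflicts with the SAP's. The extent is 0 to 6 of 20 per arm in pooled Cohorts 1 and 2 and at most 5.2% per arm in pooled clinical success, before other exclusions. This rests on taking Table 16-6 as the trial's definition of severe malaria, which the Cohort 2 to 5 exclusions support.

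A reader might infer three stronger things that the documents do not support:

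- *That milder patients pull the difference towards zero and so favour non-inferiority.* Cohort 1 is clinically milder, but the endpoint is 12-hour parasite reduction, and Cohort 1 must have at least 60,000 parasites per µl against 5,000 in Cohort 2. Nothing says that these patients respond better, and step 4 shows no consistent direction.
- *That 30% of the age 12 and over comparison is non-severe.* Prostrated Cohort 1 patients meet Table 16-6.
- *That the Cohort 2 estimate should replace the pooled one as decisive.* With Cohorts 1 and 2 complete, that would be a post hoc redesignation, and the correction does not need it.

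**What to change.** 1. In Protocol 2.1 and 2.2 and SAP 2.5.1 and 2.6.1, state the population of the pooled Cohort 1 and 2 primary estimand and of the all-cohort key secondary estimand as moderately severe or severe *P. falciparum* malaria. The primary estimand for Cohorts 3, 4 and 5 stays severe.
2. Use one PPS severity rule in Protocol 12.1 and SAP 2.2 and 5.9, namely the SAP's cohort-specific rule. Enter it in SAP section 4 as a dated change. Because Cohorts 1 and 2 are complete, also show the result under the protocol's literal rule.
3. Whenever a statement is made about severe malaria at age 12 and over, report the Cohort 2-only 90% interval (FAS and PPS, already covered by SAP 2.5.5 and 2.5.7) next to the pooled result. Leave the primary estimate as it is.
4. In the same edit, reconcile the parasite-count window in Table 5-15 with Cohort 2 eligibility. Otherwise the Cohort 2 PPS drops eligible severe patients.

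The cost is wording in both documents and one additional PPS result. No sample size changes.
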